#### 8.2.3 Secondary outcome analysis

To find the optimal threshold of FIT and VOC we will first plot the receiver operating characteristic (ROC) curves of both tests individually. The individual optimal threshold is the one that gives the greatest specificity whilst achieving the required 97% sensitivity to avoid colonoscopy or CTC. Secondly, we will plot combinations of the two tests in the ROC space and similarly, choose the combination of thresholds which has greatest specificity whilst achieving the required 97% sensitivity to avoid colonoscopy or CTC. The combined thresholds of FIT and VOC in the ROC space is done by combining every unit of FIT (from 7 to 120 µgHb/g faeces) with every unit of the predicted probability of VOC (from 0.63 to 1). Both the "or" and "and" rules will be used in combining the FIT and VOC results to define a case as positive (having SBD and requires colonoscopy) and negative (no SBD and does not require colonoscopy or CTC). The "or" rule is as described in Section 8.2.2. The "and" rule is when both FIT and VOC tests define a case as positive then the diagnosis is positive. If both tests are in discordant, i.e. only one of them defines a case as positive and the other defines it as negative then the diagnosis is negative. For each of the thresholds that we derive from the ROC curves, we will also report the NPV estimates. This will produce an overestimate of test accuracy, which we will use as a sensitivity analysis in the economic model, as a

more optimistic assumption to demonstrate the range of uncertainty. Similarly, the reference standard is the final report from the CTC or colonoscopy examination and confirmatory histology report of SBD.

Other secondary analyses include sensitivity, specificity, PPV and NPV estimates and their corresponding 95% CI for each individual condition of SBD (colorectal cancer, colorectal adenomasand inflammatory bowel disease) by each individual test and combination rules.

We will also estimate the compliance rates – return of stool and urine samples – by presence of SBD or not and individual conditions comprising SBD, as well as if samples are missing at random or not. All accuracy tests will be adjusted by covariates (demographics and/or clinical parameters) if there is an association between each covariate and the test results.

Appropriate procedures to account for the type of missing data will be performed for sensitivity analyses.

We will investigate the types of SBD and microscopic colitis, and the number of cases missed by CTC, FIT and VOC analyses. Depending on the number of microscopic colitis cases, we may explore the accuracy of FIT and VOC in detecting microscopic colitis with the other SBDs.

A full statistical analysis plan will be written and signed off prior to conducting the final analyses.

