#### 8 STATISTICS AND DATA ANALYSIS

8.1 Sample size calculation

To replace colonoscopy and CTC the new testing strategy requires very high sensitivity to avoid false negative results and missed disease. False positive results are also undesirable, but these participants would simply follow the colonoscopy testing pathway that all participants follow currently. Therefore, the sample size calculations are based on achieving acceptable sensitivity. There are some data on the utility of FIT alone and urine VOC alone in the detection of SBD(6, 10, 37). Our recent study (n=562) is the only published study that evaluated the combination of both FIT and urine VOC for the detection of colon cancer, which was 97% (95% CI: 90 to 100), similar to that for colonoscopy(6). The sensitivity of FIT alone in detecting IBD is 0.85, with the combined accuracy of FIT and VOC unknown. On the basis of these previous studies, and the necessity for high sensitivity to replace colonoscopy, we assumed that the sensitivity (Se) of the FIT and urine VOC tests to detect SBD would be at least 0.97 which is very near 1.0. The confidence interval for such high sensitivity has to be adjusted such that the interval does not exceed 1.0. One recommended method is to use the Zhou-Li method as described in equations 4.5 to

replaced by Se. Assuming that the sensitivity of FIT and VOC to be at least 97% then for Se = 0.97 and a 95% CI width of 0.05 (ensuring a high precision around the sensitivity estimate) the required number of participants with SBD is 200. Further assuming that the prevalence of SBD in the population with bowel symptoms is 19% (likely underestimate), then 1053 participants are required. Based on previous study(6) about 55% of the participants would return both stool and urine samples and sufficient for FIT and VOC analyses. Thus, the total sample size required is 1,915.

This strategy is robust to changes in the underlying assumptions of test accuracy. Confidence intervals for sensitivity for different observed sensitivity for 150, 200 and 250 cases of SBD are shown in Figure 5(a). For the target sensitivity of 0.97, the width of the confidence interval is 0.05 with 200 SBD participants, with narrower and wider confidence interval limits, when the observed sensitivity is above and below this value, respectively (Figure 5(b)).

Figure 5 Confidence intervals for different estimates of sensitivity for 150, 200 and 250 cases of SBD.

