#### 8.2.2 Primary outcome analysis

The primary outcome is diagnostic accuracy - sensitivity, specificity, NPV and PPV of the dual index test, FIT and VOC. A FIT result that is >10 µgHb/g faeces OR a VOC result with predicted probability >0.63 implies that the participant is defined as having SBD and need to be referred for colonoscopy. We will report 2x2 tables of test accuracy of the dual test by the reference standard (final report from the CTC or colonoscopy examination and confirmatory histology report of SBD which is either colon cancer, colorectal adenomas or inflammatory bowel disease), alongside summary measures of sensitivity, specificity, NPV and PPV, and their 95% confidence intervals. Confidence intervals for sensitivity and specificity estimates that are very close to 1.0 will be according to the Zhou-Li method and the intervals for NPV and PPV estimates that are very close to 1.0 will be according to the Bayesian method (38). These test accuracy estimates will be used in the economic model.

We will analyse the combined FIT+VOC test results as both parallel (results from both tests are interpreted in combination) and serial testing (VOC performed only if FIT negative, i.e. <10  $\mu$ gHb/g faeces). The "or" rule will be considered in the interpretation of both parallel and serial tests where the diagnosis is positive when either test is positive (FIT >10  $\mu$ gHb/g faeces and/or VOC predicted probability >0.63), and negative when both are negative (FIT <10  $\mu$ gHb/g faeces and VOC predicted probability <0.63). In the serial test, if the FIT is positive (FIT >10  $\mu$ gHb/g faeces) then the diagnosis is positive. Otherwise, use the result from VOC and if it is positive (VOC predicted probability >0.63) then the diagnosis is positive. If the VOC result is also negative then the diagnosis is negative. Mathematically, both methods would give the same diagnostic results but would make a difference in the economic model.

A 2x2 table of test accuracy for each individual index test by the reference test will also be presented. Sensitivity, specificity, PPV and NPV will also be presented with their 95% confidence intervals for FIT only and VOC only. Participants with missing data for either of the index tests (FIT or VOC) or the reference standard (colonoscopy) will be excluded from this analysis.

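### The combined threshold search only raises the VOC cut-off from its primary value, so under the 'or' rule it reaches 97% sensitivity only if the primary rule already does, or if FIT 7 to 9 closes the gap

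*Protocol*

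**What the plan says.** Section 8.2.3 of the protocol has two steps. In the first, "we will first plot the receiver operating characteristic (ROC) curves of both tests individually", and each test's cut-off is chosen for specificity at 97% sensitivity. No range is set for this step. In the second, the tests are combined and the plan is to "choose the combination of thresholds which has greatest specificity whilst achieving the required 97% sensitivity". The grid for the second step is fixed: "combining every unit of FIT (from 7 to 120 µgHb/g faeces") "with every unit of the predicted probability of VOC (from 0.63 to 1"). Both an 'or' rule and an 'and' rule are applied to it.

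The primary rule in section 8.2.2 is FIT above 10 µgHb/g, "OR a VOC result with predicted probability >0.63 implies that the participant is defined as having SBD". The sample size in section 8.1 rests on a high value for that combination: "we assumed that the sensitivity (Se) of the FIT and urine VOC tests to detect SBD would be at least 0.97".

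Appendix D proposes 0.63 on the strength of earlier accuracy results and expects it to be refined during the study. Section 8.2.3 accepts that the selected thresholds will give optimistic accuracy and uses them as a sensitivity analysis in the economic model. Section 2.1 calls threshold optimisation exploratory.

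**The concern.** Under an 'or' rule, raising either cut-off can only remove participants from the positive group, so sensitivity can only stay the same or fall. The VOC range begins at the primary cut-off and goes up. If the primary rule falls short of 97%, the cut-off has to move down, and the grid does not allow that for VOC. FIT has only three units of room.

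The two steps can also disagree. If the individual ROC step finds that VOC needs a cut-off below 0.63 to reach 97%, the combined step excludes that value. A floor at 0.63 also sits badly with the intention in Appendix D to refine the value.

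What is at stake is the optimal-threshold result that section 8.3 passes to the economic model. It might not exist, or it might be the best only above an arbitrary floor. The primary accuracy estimates are not affected.

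**Working it through.** **1. The plan's own figure.** Section 8.1 uses 200 SBD cases, 19% prevalence and 55% sample return. 200/0.19 = 1,052.6, so 1,053. 1,053/0.55 = 1,914.5, so 1,915. This is reproduced. A Wilson interval at 194/200 has width 0.050, in line with the stated 0.05. The Zhou-Li equations are missing from the text, so that interval was not checked. The 200 cases are used in step 5.

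**2. Ordering the grid against the primary rule.** This needs no assumption about test performance.
- 'Or' rule: Se_or(f, v) = P(FIT > f or VOC > v, given SBD). It cannot increase in f or in v, so its maximum on the grid is at FIT 7, VOC 0.63.
- 'And' rule: Se_and(f, v) ≤ Se_VOC(v) ≤ Se_VOC(0.63) ≤ Se_or(10, 0.63) for every v ≥ 0.63.

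The protocol does not define a unit of probability. With steps of 0.01 there are 38 VOC values and 114 FIT values, so 114 × 38 = 4,332 points per rule.

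| Points | Count | Against the primary rule |
|---|---|---|
| 'or', FIT 10, VOC 0.63 | 1 | is the primary rule |
| 'or', FIT 7 to 9, VOC 0.63 | 3 | at least as sensitive |
| 'or', FIT 7 to 9, VOC above 0.63 | 3 × 37 = 111 | cannot be ordered |
| 'or', the rest | 111 × 38 − 1 = 4,217 | cannot be more sensitive |
| 'and', all | 4,332 | cannot be more sensitive |

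(4,217 + 4,332)/8,664 = 8,549/8,664 = 98.7%. Each of the 111 unordered points is no more sensitive than the same FIT value with VOC 0.63. So if the primary rule is below 97%, recovery depends on FIT 7 to 9.

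**3. Bound on the 'and' rule.** Its sensitivity cannot exceed that of either test alone at the same cut-offs. Section 1.9 (Dual Testing) says 37% of SBD is FIT negative, so FIT alone is about 1 − 0.37 = 0.63. The FIT threshold behind that figure is not stated there, and the gain from FIT 10 to FIT 7 is not given. By condition, section 1.9 gives FIT sensitivities of 0.80 (cancer), 0.53 (adenoma) and 0.86 (IBD).

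**4. Where the primary rule could lie.** With FIT at 0.63, VOC must detect (0.97 − 0.63)/0.37 = 0.919 of FIT-negative SBD. Assume independence given disease, so dual sensitivity = 1 − 0.37 × (1 − s), where s is VOC sensitivity:
- s = 0.63 (cancer, Appendix D): 0.863
- s = 0.80 (cancer, section 1.9): 0.926
- s = 0.86 (IBD, section 1.9): 0.948
- s = 0.92 (adenoma, section 1.9): 0.970

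By condition, with the section 1.9 figures for both tests:
- cancer: 1 − 0.20 × 0.20 = 0.960
- adenoma: 1 − 0.47 × 0.08 = 0.962
- IBD: 1 − 0.14 × 0.14 = 0.980

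The cancer pilot, in which VOC found 6 of 7 FIT-negative cancers, gives 0.80 + 0.20 × 6/7 = 0.971. These values lie on both sides of 0.97.

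**5. Sampling variation.** Read the requirement as an observed sensitivity of at least 0.97, which is 194 of 200. With X ~ Binomial(200, Se):

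| True sensitivity | P(X ≥ 194) | P(below 0.97) |
|---|---|---|
| 0.95 | 0.124 | 0.88 |
| 0.96 | 0.308 | 0.69 |
| 0.97 | 0.606 | 0.39 |
| 0.98 | 0.891 | 0.11 |

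**6. If the primary rule passes.** The search then gives up surplus sensitivity for specificity, but only by raising cut-offs, apart from FIT 7 to 9. Any pair with VOC below 0.63 and FIT above 10 is never examined, although such a pair could meet 97% with better specificity. The protocol has no data to show whether one does.

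**The case against.** The best defence is that the grid contains the primary rule and section 8.1 assumes that rule reaches at least 0.97. On that assumption, searching upward is coherent, because it asks how much specificity can be bought with spare sensitivity. This stands. A reader might infer that the search cannot find a 97% combination, or will probably return nothing. The protocol does not support that: failure depends on the primary rule falling short, and if it is near 0.96 the step to FIT 7 to 9 could be enough.

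A reader might also try to calculate how far below 0.63 the VOC cut-off must go, for instance from the AUC of 0.67 in Appendix D. That is not supported either. The AUC is for cancer, not SBD. The score is a neural-network output scaled to 0 to 1, with no calibration or prior given. The reported VOC sensitivities are not tied to a probability cut-off of 0.63: Appendix D pairs adenoma sensitivities of 0.93 and 0.91 with specificities of 0.16 and 0.15, so different operating points lie behind these figures.

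The defence can add that the individual ROC step has no range limit, that the analysis is exploratory with its optimism acknowledged, and that the economic model also uses the primary thresholds. All of this lowers the stakes. It does not explain why the combined search should stop at 0.63. Nor is this a detail left open for the SAP, because the protocol states the range.

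**Conclusion.** The concern holds in a conditional form. The combined search is one-sided in VOC, and 98.7% of its points cannot be more sensitive than the primary rule. Under the 'or' rule it reaches 97% only if the primary rule does, or if FIT 7 to 9 makes up the difference. On the FIT figures in section 1.9, no 'and' combination is expected to reach 97%. When the primary rule does pass, the selected pair may still not be the most specific one available.

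The ordering is pure set logic; only the count depends on the assumed 0.01 step. The range of 0.86 to 0.97 rests on independence given disease and on applying condition-specific VOC sensitivities to SBD as a whole. The 39% rests on exactly 200 SBD cases, a true sensitivity of 0.97 and reading the requirement as a point estimate. The primary rule's true sensitivity is unknown. The change is worth making, but it concerns an exploratory analysis.

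**What to change.** In section 8.2.3, search VOC over the full range 0 to 1 in a stated step, for example 0.01, and FIT from the lowest reportable value to 120 µgHb/g. Keep the 97% constraint and the choice by specificity. Add that if no 'and' combination meets the constraint, this will be reported as the result.

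The cost is one or two sentences and more computation. Even with FIT still starting at 7, the grid grows from 4,332 to 114 × 101 = 11,514 points per rule. No new data are needed and the primary analysis is untouched. The downside is somewhat more selection optimism from the larger search. Section 8.2.3 already acknowledges that optimism, so an optimism-corrected estimate at the chosen pair is useful but optional.

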8.3 Economic evaluation

An economic analysis will be carried out to determine the costs, benefits and overall cost-effectiveness of FIT + VOC versus FIT followed by colonoscopy or CTC in participants with gastrointestinal symptoms referred for investigation.

As recommended, and in order to meet the needs of NICE for a future technology appraisal, the analysis will be carried out principally from the perspective of the NHS and Personal Social Services (PSS) and it will employ a decision analytic model built as part of this study. Should relevant data be available, additional analyses will consider wider costs that are likely to differ between the compared options, including productivity loss resulting from time taken off paid employment (40, 41).

A review of the literature will be carried out to identify existing decision models used in the broader clinical area, insights from which will inform the structure of a de novo decision model tailored to address the particular decision problem. A preliminary review of the literature has identified only a few relevant decision models, the key one being the model developed as part of NICE Guidance on recognition and referral of suspected cancers (NICE Guideline NG12) (42). This work has informed two more recent models investigating the cost-effectiveness of FIT test as a diagnostic aid for colorectal cancer referrals in primary care commissioned by NICE  and the NIHR Health Technology Assessment programme (7). All of these models have employed a multi-part structure, and at this stage, it is envisaged that our model will follow a similar structure, as this is suitable for delineating and capturing short and long-term costs and consequences (accruing over a lifetime horizon). In particular, it is possible that the model will consist of the following three parts:

- (i) a decision tree delineating and modelling the short-term cost and consequences (life years and QALYs) resulting from the possible findings (diagnoses) following the use of each diagnostic option
- (ii) a simple state-transition model capturing the long-term costs and consequences accruing over a life-time horizon, associated with the treatment and progression of SBD, and
- (iii) a simple state-transition model reflecting long-term costs and consequences in participants without SBD.

IRAS 282247\_RECEDE protocol\_v2.2\_11.02.2022 Page 29 of 50

The first two parts of the model will be run for each of the conditions classified as SBD (i.e. colorectal cancer, colorectal adenomas and inflammatory bowel disease).

Calculations will consider all key costs and consequences, including the costs and 'disutility' associated with having a colonoscopy or CTC. Model input will be drawn from relevant sources, including the RECEDE study and the available literature. For example, parameters related to the diagnostic characteristics of the compared options—which will be a key input in the first part of the model and a crucial parameter for the overall analysis—will be collected directly from RECEDE (we will model the accuracy at the thresholds pre-specified in the primary outcome, and the optimal thresholds from the exploratory analysis). Further information for the economic model, such as estimates of the rate of adverse outcomes associated with colonoscopies (e.g. bowel perforation and bleeding) or CTCs, preference-based health-related quality of life (utility) values and primary and secondary care resource use for the diagnostic part of the model will be collected from a sample of 370 RECEDE participants (20% of the total intended sample) recruited at UHCW. The questionnaires will continue to be administered until 370 participants have completed all five of their questionnaires.

In planning the study, we considered carefully whether collecting information on the 'disutility' of colonoscopy from patients at one site would introduce any unanticipated bias. We believe that the nature of the data we are interested in (impact of colonoscopy or CTC on patient's quality of life over the short time period before and after the procedure) and the fact that colonoscopy and CTC procedures and the preparation stage preceding them is well defined and standardised across NHS settings, makes it unlikely that single site data collection will results in any unanticipated bias or unrepresentativeness. Given this, and the fact that other sites indicated that further data collection (quality of life questionnaires) might be a barrier to recruitment, we felt that collecting data from a single site is sensible and justifiable.

Costs associated with the compared diagnostic options (including the costs of the diagnostic tests, colonoscopies, CTCs and subsequent staging and treatment in primary and secondary care) will be obtained from manufacturers, the available literature and published sources (including the most recent NHS Reference Cost Schedules, the latest Unit Cost of Health and Social Care report and the British National Formulary). Additional preference-based quality of life ('utility') estimates to be used in the model (e.g. long-term 'utility' values associated with different stages of colorectal cancer or SBD in part (ii) (43) and age and gender specific 'utility' values for the healthy general population in part (iii)(44,45) will be obtained from the relevant literature.

Undergoing a colonoscopy, including the bowel preparation and the procedure itself, will usually mean loss of usual activities (typically for 2-3 days) in addition to experiencing unpleasant symptoms. Participants undergoing a colonoscopy need to follow a low fibre diet for two days prior to the examination and are required to take laxatives the day before. This will lead to frequent, watery diarrhoea and occasional incontinence; thus the process is associated with discomfort, anxiety and affects participants' ability to go about their usual activities. Though CTC is often preferred by patients, it still requires bowel preparation to be completed, and the procedure itself can still be invasive and uncomfortable. Whilst evidence suggests that people are averse to having a colonoscopy, specific evidence on the 'disutility' of a colonoscopy or CTC examination, presented in the form of decrements in preference-based quality of life which can be used in an economic evaluation is scarce. Searches in the literature have highlighted a paucity of evidence, thus the RECEDE study will offer an opportunity to collect individual participant data.

Information on the disutility of colonoscopy and CTC will be captured alongside the collection of HRQoL and resource use for the diagnostic part of the model. This will involve administering the EQ-5D-5L questionnaire to the sample of 370 participants scheduled to undergo colonoscopy or CTC. The collected information will enable us to obtain insights into the impact of the procedure (including the preparation) on participants' quality of life, which is an important parameter in the cost-effectiveness analysis. The

IRAS 282247\_RECEDE protocol\_v2.2\_11.02.2022 Page **30** of **50** 

EQ-5D is a widely used generic measure of health-related quality of life that enables the calculation of QALYs and is recommended for use in economic evaluations in health care (47,48). The descriptive part of the EQ-5D-5L questionnaire (which comprises questions on mobility, self-care, usual activities, pain/discomfort, anxiety/depression) and the accompanying visual analogue scale ask participants about their quality of life on the particular day and will be administered at (i) baseline (i.e. when participant consent is received) (ii) immediately prior to colonoscopy or CTC once the participant has fully completed bowel preparation, (iii) 24 hours after the colonoscopy or CTC examination, (iv) 72 hours post colonoscopy or CTC and (v) 3 weeks post colonoscopy or CTC. Collected data from the EQ-5D-5L (5-digit numbers describing the respondent's health state at different points in time) will be subsequently translated into preference-based health related quality of life indices using available value sets (49, 50).

In line with recommendations, final results will be presented in terms of total costs (discounted at 3.5% per annum) per additional QALY associated with each of the compared options (51). Deterministic and probabilistic sensitivity analyses will be undertaken to explore the robustness of the obtained results to sample variability and plausible variations in key assumptions and employed analytical methods . The model will also form the basis for conducting value of information analysis, which will quantify the total expected cost due to the remaining uncertainty around the decision problem (53, 54).

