#### CTC or Colonoscopy appointment

EQ-5D-5L and Resource Use Questionnaire **before** colonoscopy Complete CTC or colonoscopy

EQ-5D-5L Questionnaire 24 hours after colonoscopy or CTC EQ-5D-5L Questionnaire 72 hours post colonoscopy or CTC

EQ-5D-5L and resource use questionnaire 3 weeks post colonoscopy or CTC Adverse outcomes follow up

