#### SCHEDULE OF EVENTS

**Table 1** Schedule of events for collection of stool FIT and urine VOC for both face-to-face and remote
 recruitment scenarios.

Face to Face:

Observation	Baseline (referral visit)	Day of colonoscopy or CTC (before procedure)	24hrs & 72hrs post colonoscopy or CTC	3 weeks post colonoscopy or CTC	Analysis complete and results available
Eligibility screening					
	Х				
Informed consent	Х				
Baseline data	Х				
Urine sample for VOC analysis	Xª				
Stool sample for FIT test	Xp				
Participant questionnaires: EQ-5D*	Xc	х	Xc	Xc	
Resource use questionnaire*		х		Xc	
Colonoscopy or CTC					
results and adverse				Х	
outcomes					
Follow Up in CTC					Х
negative patients					

Remote:

Observation	Baseline (remotely)	Pre- colonoscopy or CTC (participant at home)	Day of colonoscopy or CTC (before procedure)	24hrs and 72hrs post colonoscopy or CTC	3 weeks post colonoscopy or CTC	Analysis complete and results available
Eligibility screening	х					
Informed consent	X (via telephone)					
Baseline data	Х					
Urine sample for VOC analysis (kit to be posted to participant)		Xď				
Stool sample for FIT test (kit to be posted to participant)		Xp				

Participant	VC	V	M	XC	
questionnaires:	Xc	Х	Xc	Xc	
EQ-5D*					
Resource use		V		VC	
questionnaire*		Х		Xc	
Colonoscopy or					
CTC results and				х	
adverse				^	
outcomes					
Follow Up in CTC					Х
negative patients					

Note - all sample collections are designed to be timed, if possible, with participant's attendance to clinic or treatment to minimise additional visits. If this is not feasible, there is a postal option or delivery to local GP for transport to central site only\*

- (a) If participant is unable to provide a urine sample at Baseline, they can return sample to their GP surgery\* or drop it off at the hospital. If this is not possible, participants also have the option to collect a urine sample, 24 hours prior to bowel prep, and bring it with them on the day of colonoscopy/CTC (participant will have to keep the sample in the freezer and, if required, place in a provided cool bag when bringing back to the hospital if sample is likely to be out the freezer for over 1 hour)
- (b) Only provide participant with FIT testing kit and pre-paid envelope for stool sample collection at home if it will be 4 weeks between their first referral FIT test and their colonoscopy/CTC appointment.

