- (c) Both paper, electronic and telephone versions of questionnaires will be made available depending on site and participant preference. If a paper option is preferred, provide the participant with a pre-paid envelope to return questionnaire(s) or collect on the day of colonoscopy or CTC if possible.
- (d) Provide participant with VOC testing kit and optional cool bag (if required) for urine sample collection at home. Also provide pre-labelled envelope if returning their sample via their GP courier service.
- (e) Participants medical records will be checked prior to contacting participant for follow up

\*Note –questionnaires only to be requested at sponsor site (UHCW)

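### Section 8.3 takes colonoscopy and CTC adverse-outcome rates from 370 single-site questionnaire participants, although adverse outcomes are scheduled without that restriction

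*Protocol*

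**What the plan says.** One sentence in section 8.3 assigns three model inputs to the same subset: utility values, primary and secondary care resource use, and "estimates of the rate of adverse outcomes associated with colonoscopies (e.g. bowel perforation and bleeding) or CTCs". All three "will be collected from a sample of 370 RECEDE participants (20% of the total intended sample) recruited at UHCW". The subset is filled by a rule about forms: "The questionnaires will continue to be administered until 370 participants have completed all five of their questionnaires". The last of the five falls at "v) 3 weeks post colonoscopy or CTC".

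Section 8.3 then defends using a single site. The data of interest are described as the "impact of colonoscopy or CTC on patient's quality of life over the short time period before and after the procedure", preparation and procedures are said to be standardised across the NHS, and other sites had indicated that quality-of-life questionnaires might hinder recruitment.

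Elsewhere adverse outcomes are handled separately from the questionnaires. In both the face-to-face and the remote version of Table 1, the row for colonoscopy or CTC "results and adverse" outcomes is marked at 3 weeks and has no asterisk. The asterisk sits on the EQ-5D and resource-use rows, and its footnote reads "questionnaires only to be requested at sponsor site (UHCW". The flow chart lists "Adverse outcomes follow up" as a step of its own, and its note limits only the EQ-5D-5L to the sponsor site.

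**The concern.** Utilities and resource use can only come from people who fill in forms, so a questionnaire subset is the right source for them. A perforation or bleed is recorded whether or not a form is returned, and the schedule provides for that record at every site. Naming the 370 as the source discards most of the available denominator for the model's rarest input.

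Neither reason given for a single site carries over. Questionnaire burden does not apply, and the argument about short-term quality of life does not address complication rates. Section 1.6 suggests that site could matter: it says older patients with comorbidities are at higher risk during colonoscopy, and that some Trusts now use CT for all referrals. Case mix and modality therefore differ between hospitals.

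At stake is how well the model values procedure harm avoided. Appendix E Table 3 lists patient morbidity among the costs of investigating everyone.

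**Working it through.** **Denominators.** The total reproduces from section 8.1: 200 / 0.19 = 1,052.6, so 1,053; 1,053 / 0.55 = 1,914.5, so 1,915. The subset of 370 is from section 8.3.

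**Assumed input.** The protocol gives no complication rate, so r is taken over 0.05% to 1%.

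**Expected events** = n × r. **Chance of seeing none** = (1 − r)^n.

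| Assumed r | Expected, n = 370 | Expected, n = 1,915 | P(none), n = 370 | P(none), n = 1,915 |
|---|---|---|---|---|
| 0.05% | 0.185 | 0.96 | 83% | 38% |
| 0.1% | 0.37 | 1.92 | 69% | 15% |
| 0.2% | 0.74 | 3.83 | 48% | 2% |
| 0.5% | 1.85 | 9.58 | 16% | <0.1% |
| 1% | 3.70 | 19.15 | 2% | <0.1% |

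**Upper limit with no events** (one-sided 95%) = 1 − 0.05^(1/n):

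- n = 370: 0.81%
- n = 1,915: 0.16%
- n = 1,053 (a pessimistic case: only 55% of the cohort has a usable record, borrowing the protocol's sample-return fraction): 0.28%, still about 0.81 / 0.28 = 2.9 times tighter than with 370.

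The relative standard error falls by √(1,915 / 370) = 2.3 when the whole cohort is used.

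**By modality.** The CTC share is not given. Section 1.6 says over 25% of referrals have CT scans, which is only a proxy. Same formula, two assumed splits:

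- 75/25: colonoscopy 278 against 1,436, limits 1.07% and 0.21%; CTC 92 against 479, limits 3.2% and 0.62%.
- 50/50: 185 against 958 for each modality, limits 1.6% and 0.31%.

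**Conditional check on selection.** This applies only if the 370 are read as people who completed all five forms. Let those with a complication complete k times as often as others. The rate among completers is then rk / (rk + 1 − r). With r = 0.5%:

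- k = 0.5: 0.0025 / 0.9975 = 0.25%
- k = 0.25: 0.00125 / 0.99625 = 0.13%
- k = 1.5: 0.0075 / 1.0025 = 0.75%

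The protocol gives no value for k, so this shows only that completion settled after the procedure can shift the rate.

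**The case against.** The strongest reply is that the sentence matters less than it appears to. Section 8.3 says in general terms that model inputs come from RECEDE and from the literature, and the disputed sentence does not exclude published complication rates. The section also commits to deterministic and probabilistic sensitivity analysis and to value-of-information analysis, so a wide interval would be propagated rather than hidden. This stands as mitigation. It does not name another source for this parameter, and it would not justify leaving scheduled data out.

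A second reply is that complete data from all sites are not assured. Collection everywhere is inferred from a row without an asterisk and a flow-chart step. Section 7 does not describe how adverse outcomes are ascertained, section 7.6 expects some participants not to attend, and section 9.1.3 covers only events caused by study activity. This also stands: 1,915 is a ceiling, and a reader should not infer that a known number of usable records is being thrown away.

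Third, the whole cohort would itself be thin for very rare events (about one expected at 0.05%). That is true, and is why published rates belong in the fix.

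A reader might also infer that non-completers' adverse outcomes are dropped and that the resulting rate is too low. The text does not support this. The completion rule says when questionnaires stop being handed out. Elsewhere in 8.3 the 370 are described as people scheduled for a procedure. Nothing says an adverse outcome is ignored when a form is missing, and no evidence is given on how complications affect completion.

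**Conclusion.** The point holds as a minor one. Section 8.3 ties procedure adverse-outcome rates to 370 sponsor-site questionnaire participants, while the schedule and flow chart place adverse outcomes outside the sponsor-site restriction and the single-site rationale does not reach them. The loss is precision and representativeness in one input to a secondary economic analysis; the primary accuracy results are untouched.

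The zero-event comparison (0.81% against 0.16%) needs no assumed complication rate, but the second figure assumes that all 1,915 have the procedure and a record. The expected-event figures rest on the assumed range: the 370 would yield fewer than two events at rates up to 0.5%, while near 1% the case weakens, with about four expected. Selection through questionnaire completion is a possibility under one reading of the text, not a demonstrated bias.

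**What to change.** Reword section 8.3 so that adverse-outcome rates are estimated separately for colonoscopy and CTC, from all participants at all sites who have the procedure and a 3-week adverse-outcome record, regardless of questionnaire completion. State that these rates are combined with published rates in the probabilistic analysis. Keep the 370 for EQ-5D-5L and resource use only.

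No new data item or visit is needed. The cost is that every site must complete the already scheduled 3-week adverse-outcome record in a uniform way.
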